9.1.6 Unexpected Adverse Event or Suspected Adverse Reaction

An AE or SAR is considered “unexpected” if: it is not listed in the investigational brochure (IB); or, it is not listed at the specificity or severity that has been observed; or, if an IB is not required, it is not consistent with the risk information described in the general investigational plan. “Unexpected” also refers to AEs or SARs that are mentioned in the IB as occurring with a class of drugs or as anticipated from the pharmacological properties of the drug, but are not specifically mentioned as occurring with the particular drug under investigation.

9.2 Serious Adverse Events

A serious adverse event (SAE) is any AE or SAR that results in any of the following outcomes:

1. Death;
2. A life-threatening AE (this refers to an event in which the patient was at risk of death at the time of the event and not to an event which hypothetically might have caused death if it were more severe.);
3. In-patient hospitalization;
4. Prolongation of existing hospitalization;
5. A persistent or significant incapacity or substantial disruption of the ability to conduct normal life functions;
6. A congenital anomaly/birth defect;
7. An important medical event that may not be immediately life-threatening or result in death or hospitalization but may jeopardize the patient and may require medical or surgical intervention to prevent one of the other outcomes listed in this definition.

Serious adverse events should not be reported for hospitalization or prolonged hospitalization in the following scenarios: for a diagnostic or elective surgical procedure related to a pre-existing condition; to allow for an efficacy measure for the study; or, for a planned surgical procedure that was not the result of a condition worsening due to participation in the study.

When reporting AEs, SAEs, or SARs, the Investigator should avoid colloquialisms and abbreviations and use correct medical terminology. Additionally, if known at the time of reporting, a diagnosis should be reported rather than individual signs and symptoms. If a

diagnosis is unknown at the time of initial reporting but subsequently established, it should be reported as follow-up information.

Pre-existing medical conditions are reported as AEs or SAEs only if the frequency, severity, or character of the condition worsens during the study. When reporting such events, it is important to convey the concept that the pre-existing condition has changed by including applicable descriptors.

9.3 Reporting Adverse Events from Participating Clinical Sites

Safety assessments will consist of monitoring and reporting all adverse events from the start of the initial study drug infusion through 24 hours following the final infusion of study drug (typically Day 5) or for 24 hours following the final infusion of study drug for those patients who do not complete the entire course of study drug administration. Adverse events that do not meet the definition of “serious” or “suspected adverse reactions” will be reviewed periodically throughout the trial to identify any previously unidentified trends or other safety issues.

In order to ensure prompt reporting of adverse events, we require that all non-serious adverse events must be entered into the WebDCU™ database system within 5 working days following the completion of Treatment Day 1-T0 through 24 hours Following the Completion of the Last Infusion study phases (e.g., Day 1 phase is Tuesday, 02JAN2012; any AEs occurring in that phase must be entered into the WebDCU™ database system no later than Monday, 09JAN2012).

9.4 Reporting Serious Adverse Events and Suspected Adverse Reactions from Participating Clinical Sites

With regard to serious adverse events and suspected adverse reactions, both expected and unexpected and regardless of whether the SAE/SARs are considered related to the study drug and/or the disease, they will be followed in a rigorous review process through the entire trial period. Clinical performance sites are instructed to report all fatal events, unanticipated problems and other serious adverse events and suspected adverse reactions in the WebDCU™ database system **within 24 hours of first knowledge of the event**. Additionally, all current study data for that particular patient must be entered to allow for timely review by the Internal Medical Monitor (IMM) and the independent external Medical Safety Monitor (MSM). In adjudicating cases at UT Southwestern, an alternate IMM will serve in place of the IMM.

The clinical site Investigator, on the basis of his or her clinical judgment and the following definitions, determines the relationship of the adverse event to the protocol intervention as one of the following:

- Definitely: any adverse reaction and those adverse events that cannot be reasonably explained by an alternative explanation, e.g., concomitant drug(s), concomitant disease(s). The relationship in time is very suggestive, e.g., it is confirmed by de-challenge and re-challenge.
- Probably: An AE that might be due to the use of the study agent. The relationship in time is suggestive, e.g., confirmed by de-challenge. An alternative explanation is less likely,

e.g., concomitant drug(s), concomitant disease(s); and, other causes have been eliminated or are unlikely.

- Possibly: An AE that might be due to the use of the study drug. An alternative explanation, e.g., concomitant drug(s), concomitant disease(s) is inconclusive. The relationship in time is reasonable; therefore, the causal relationship cannot be excluded and while other potential causes may or may not exist, a causal relationship to the study drug does not appear probable.
- Unlikely: An AE for which an alternative explanation is more likely, e.g., concomitant drug(s), concomitant disease(s), and/or the relationship in time suggests that a causal relationship is unlikely or that there is a clear alternate cause that is more likely to have caused the adverse event than the study drug.
- Not related: An AE for which there is no possible relationship (i.e., the temporal relationship between drug exposure and the adverse event onset/course is unreasonable or incompatible; or a causal relationship to study drug is implausible).

The clinical site investigator in making determinations of the severity of the adverse event should consider the following for the four classes of severity of the event as it occurred:

- Mild/Grade 1: does not interfere with daily living and no medications are needed to relieve event;
- Moderate/Grade 2: somewhat interferes with daily living or medications needed to relieve event;
- Severe/Grade 3: incapacitating, activities of daily living are prohibited because of the event;
- Life threatening or Death/Grade 4.

Serious adverse events and suspected adverse reactions are collected from the start of the time of enrollment through study completion, i.e., Day 30, death, or withdrawal of consent.

9.5 Review of Serious Adverse Events and Suspected Adverse Reactions

Upon entry of a serious adverse event or suspected adverse reaction in the WebDCUTM system, the system triggers automatic e-mail notification of the SAE/SAR to the Project Manager and the IMM. When the SAE/SAR report has been reviewed and deemed to be adequate, the SAE/SAR is forwarded by the Project Manager to the MSM.

The MSM conducts independent reviews of all SAEs and SARs entered into WebDCUTM. Should the IMM or MSM need additional patient data to conduct his/her review, those data may be accessed on the WebDCUTM. The MSM submits his/her opinion on whether the SAE or SAR was (a) in fact, serious, (b) unexpected, and (c) related (with reasonable possibility) to the study drug within 72 hours of notification of the SAE or SAR. The MSM may contact the site for more information or discussion. Should it be determined that the narrative included in the SAE/SAR needs to be amended or enhanced, the SAE/SAR case report form will be returned electronically to the clinical site investigator for enhancement or amendment. If the Investigator and the MSM believe the SAE or SAR is serious, study drug-related (reasonable possibility, probably or definitely), and unexpected, the SAE or SAR requires expedited reporting. When

there is disagreement between the Investigator and the MSM on one or more of these criteria, the SAE or SAR will be reviewed by the IMM as the arbiter as to expedited reporting.

9.6 Expedited Reporting of Serious Adverse Events or Suspected Adverse Reactions

[figure not shown]
When it is confirmed that an event requires expedited reporting, the Project Manager (PM) contacts the site with instructions for completion of a safety report form. A safety report form (pre-populated with previously entered CRF data) is automatically posted in the WebDCU™ system and the site staff enters any remaining required information. Following the site's completion of the safety report form, the PM submits the report to the FDA within the regulatory timelines. The initial safety report for a SAE/SAR that was fatal or life-threatening will be submitted to the FDA within 7 days of the Executive Committee being made aware of the SAE; if the event was not life-threatening or did not result in death, the report will be submitted to the FDA within 15 days of the Executive Committee being made aware of the SAE/SAR.

The safety report filed with the FDA is posted on the WebDCU™. The PM notifies, via email, the Safety Review Committee (SRC), Ocera Therapeutics, Inc., the Trial Executive Committee members and all participating clinical site PIs and Study Coordinators (SCs) that an expedited safety report has been filed with the FDA and is available for review on the WebDCU™ (a link to the document is provided in the email communication). Each clinical site PI is then responsible for reporting to the IRB at that individual clinical site.

Follow-Up Reporting of Expedited Serious Adverse Events/ Suspected Adverse Reactions

After the submission of the initial safety report, the clinical site staff is responsible for obtaining any follow-up information about the SAE/SAR. All follow-up information should be actively sought by the clinical site staff and must be entered in the database as soon as the information becomes available. The PM distributes the follow-up safety report to all parties receiving the initial report.

Study SAE Reporting and Monitoring Flowchart

9.7 Safety Review Committee

The Safety Review Committee (SRC) will consist of three experienced ALFSG clinicians and a clinical pharmacologist with experience in clinical trials and PK measurement. All are independent of any clinical site participating in the trial and will exercise oversight of the safety of trial participants, review periodic safety reports prepared by the SDCC biostatistician, request additional data/information (if necessary), and advise the trial Sponsor and Executive Committee regarding continuation/discontinuation of the study. A primary responsibility of the SRC is to review the safety and PK data (as provided by the SDCC) and to provide recommendations on proceeding to the next dose level.

Throughout the trial the SRC will review all safety data at regular intervals and after each dose level in each cohort. In addition, the SRC will review safety and PK data for the evaluable Cohort 1 patients who complete Dose Levels 1 and 2 to determine if it is safe to enroll Cohort 1 patients into Dose Level 3 and Cohort 2 patients into Dose Level 1. Another review will be conducted prior to enrolling Cohort 2 patients into Dose Level 3. During these two specific reviews, enrollment will be paused. The SRC will also review the safety and PK data for the evaluable Cohort 2 patients who complete Dose Level 3 to determine if it is safe to enroll Cohort 2 patients into Dose Level 4. Upon completion of the study, the SRC will review safety data for all enrolled patients.

In addition to the SRC review, the IMM in consultation with the external MSM will closely monitor the incidence rates of all adverse events reported and will alert the SRC if a trend is observed for AEs collected from Baseline through the 24 hours Following the Completion of the Last Infusion period and for SAEs collected from Baseline through the Day 30 post treatment period. A summary of all AEs and SAEs, a summary of all expedited safety reports, and a listing of all patients who were terminated from the study due to study-related adverse events, will be included in reports submitted by the SDCC to the Executive Committee, the MSM, and the SRC. An annual report will be submitted to the FDA.

9.7.1 Trial Stopping Criteria

An apparent, consistent and persistent evidence of net harm that tends to overwhelm any benefit may allow for premature termination of the study.

Continuing enrollment into each dose level of each cohort will be determined on an ongoing basis and at periodic intervals as outlined in Section 9.7. The SRC will receive a report on all reported AEs and SAEs as well as the individual listings of patient with any specific event of interest. The finding of any unexpected SAEs of Grade 3 that are considered not related to acute liver failure in 2 or more patients within a given dose level or of Grade 4 or higher in one patient will lead to suspension of recruitment and review of the complete data by the MSM. Following the MSM's review, the safety report (and any comments from the MSM) will be sent to the SRC. The SRC will make the final recommendation for early termination versus continuation of the study after reviewing the available data. The decision will be guided by safety.

If the SRC does not stop the trial, the trial will proceed with enrollment as outlined in section 9.7 for Cohorts 1 and 2. In addition to the planned evaluations, the MSM and SRC will receive

quarterly safety summary reports of enrollment, baseline demographics, withdrawals from treatment and all AEs and SAEs with information on relation to study treatment.

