Study Design	
This is a Phase 2a, multi-center, open-label study, conducted in two cohorts of patients diagnosed with acute liver failure/severe acute liver injury (ALF/ALI) who meet inclusion/exclusion criteria. Cohort 1 is defined as patients with ALF/ALI with minimal renal dysfunction at the time of enrollment (defined as a serum creatinine ≤ 1.5 mg/dL and mean arterial pressure of >65 mm Hg). Cohort 2 is defined as patients with ALF/ALI with compromised renal function (defined as a serum creatinine >1.5 mg/dL and <10 mg/dL with mean arterial pressure of >65 mm Hg).
 
Informed consent will be obtained from the patient and/or patient's legally authorized representative (LAR) or family member as defined in 21CFR50.3(m). All patients will receive medical care for acute liver failure/severe acute liver injury according to the institution's standards of care. Standard of care may include, but is not limited to, administration of N-acetylcysteine and consideration for orthotopic liver transplantation.
 
Up to 36 evaluable patients will be enrolled. An evaluable patient is one who has received an infusion of OCR-002 for at least 72 hours. It is expected that not every enrolled patient will be treated for at least 72 hours due to transplant, death or early hospital discharge. Due to this, we anticipate 25% of the enrolled population will fail to reach evaluable status. Therefore, we plan to enroll up to 50 patients in order

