Treatment Continued	
experiences CTCAE grade 1 or 2 adverse reactions or intolerance to the assigned dose, the investigator may choose to titrate back to the lower tolerated dose and closely monitor the patient. The infusion rate and dose may be discontinued if the patient experiences CTCAE grade 3 or higher, or any time at the investigator's discretion. Each dose level between 1 and 3 will be administered to Cohort 1 patients and safety and PK data reviewed, prior to exposing Cohort 2 patients to the study drug and subsequent dosing levels. Dose level 4 will be administered to both Cohort 1 and 2 beginning simultaneously.
 
The dosing levels for Dose Levels 1 through 3 are defined follows:
 
Dose Level 1:
 
Patients will receive the initial infusion of study drug at 0.139 g/h for the first 12 hours (approximately 3.33 g/24h or 6.9 mL/h) and be maintained at this rate for up to 5 days.
 
Dose Level 2:
 
For patients assigned to this dose level, the infusion will be initiated at 0.139 g/h for the first 12 hours (approximately 3.33 g/24h) and increased to 0.277 g/h (approximately 6.65 g/24h or 13.8 mL/h) for the remainder of the treatment period.
 
Dose Level 3:
 
For patients assigned to this dose level, the infusion will be initiated at 0.139 g/h for the first 12 hours (approximately 3.33 g/24h), increased to 0.277 g/h (approximately 6.65 g/24h) for the next 12 hours, and then increased to 0.416 g/h (approximately 10 g/24h or 20.8 mL/h) for the remainder of the treatment period.
 
The dosing level for Dose Level 4 is defined follows:
 
Dose Level 4:
 
For patients in Cohorts 1 and 2, the infusion of OCR-002 will be initiated at 20g/24hr for a maximum time of 120 hours (approximately .83g/h), provided the dose level is well tolerated with no noteworthy side effects.
 
Initiation of each higher dose for patients in Dose Levels 1 through 3 and continuation of study drug administration for patients in Dose Level 4 will occur only if there are no treatment emergent SAEs of CTCAE Grade 4 or higher that are not attributed to acute liver failure in the opinion of the investigator.
 
In all dose levels, if 1 out of the 3 patients within a dose group experiences a treatment emergent SAE of CTCAE Grade 3 that is not attributed to acute liver failure, then an additional patient will be enrolled into that specific dose group. Within a given dose level, if 2 or more patients experience a treatment emergent SAE of CTCAE Grade 3 that is not attributed to acute liver failure in the opinion of the investigator, then dose escalation (Dose Levels 1 through 3) or continuation of study drug administration (Dose Level 4) will stop. Dose escalation or continuous administration also will stop if 1 patient experiences a Grade 4 or higher SAE that is not attributed to acute liver failure in the opinion of the investigator. Otherwise, dose escalation and continuous study drug administration will continue to the maximum tolerated dose and the remaining enrolled patients will be treated at this dose. Further details of dose

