In aggregate, these studies supported an initial study using a 10g/24 hours dose of OCR-002 as suitable for an early phase study in ALF patients. As STOP-ALF represents the first study of OCR-002 conducted in patients with ALF, the administration of the study drug in three ascending dose levels (Dose Levels 1 through 3) will be implemented as follows and in the protocol for up to 24 evaluable subjects:

The maximum target infusion rate will be 0.42g/h, which is equivalent to 10g administered over 24h.

The infusion rate will be staged for each patient. The initial infusion rate will be 0.14g/h (33% of target dose). The dose will be then increased to 0.28g/h (66% target), and 0.42g/h (100% target) in successive 12h intervals based on a patient safety evaluation by the Investigator.

Patient safety and tolerability at an increased loading dose are supported by the pharmacokinetic data and plasma ammonia levels obtained from the ongoing clinical study Phase 2 OP-GIB conducted in Spain, in which cirrhotic patients with active gastrointestinal hemorrhage receive double-blind treatment, i.e., placebo or OCR-002 at 10 g per 24 hours as a constant intravenous infusion for 5 days.

Ocera began over a year ago a large ongoing trial of OCR-002 in hospitalized patients with cirrhosis and associated hyperammonemia (OCR002-HE209, STOP-HE). In STOP-HE, a placebo-controlled, randomized, double-blind clinical trial designed to evaluate the safety, pharmacokinetics and efficacy of intravenously-administered OCR-002 in resolving neurocognitive symptoms of acute HE in hospitalized cirrhotic patients with elevated ammonia, either OCR-002 or placebo is administered to patients intravenously for up to five days along with standard of care, at doses of 20, 15, or 10 grams over 24 hours based on the patient's degree of liver impairment. In this study, there is no ascending or loading dose being implemented.

Therefore, up to 12 additional evaluable patients will be enrolled at Dose Level 4 as listed below:

Dose Level 4: For patients assigned to this dose level, the infusion will be initiated at the full dose level of 20g/24hr for a maximum time of 120 hours (approximately .83g/h), provided the dose level is well tolerated with no noteworthy side effects.

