6.3.2 Enrollment

Patients will be considered enrolled into the study once informed consent has been obtained, all eligibility criteria are met, and the study drug infusion has been initiated. A study identification number will be assigned by the computer system that houses the study database. A Screen Failure Log will be maintained to capture basic information on all patients screened for the study but who failed to be enrolled. This would include demographic information and the reasons for failure to enroll.

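### The recruitment-suspension rule in Section 9.7.1 counts only unexpected SAEs, the synopsis stopping rule counts all, and Sections 9.1.2 and 9.1.6 can class one event as both expected and unexpected

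*Combined protocol and SAP*

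**What the plan says.** **Synopsis, Treatment.** For each dose level the condition reads "if 2 or more patients experience a treatment emergent SAE of CTCAE Grade 3 that is not attributed to acute liver failure", as judged by the investigator. The consequence is that "dose escalation (Dose Levels 1 through 3) or continuation of study drug administration (Dose Level 4) will stop". The same stop applies "if 1 patient experiences a Grade 4 or higher SAE that is not attributed to acute liver failure in the opinion of the investigator". Expectedness is not mentioned.

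**Section 9.7.1.** The trigger is "any unexpected SAEs of Grade 3 that are considered not related to acute liver failure in 2 or more patients", counted per dose level. For the higher grades and the action, the sentence reads "or of Grade 4 or higher in one patient will lead to suspension of recruitment and review of the complete data by the MSM". The Medical Safety Monitor (MSM) passes the report to the Safety Review Committee (SRC), which makes the final recommendation.

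**Section 5.2** sends the reader to Section 9.7 for escalation and stopping. The synopsis count rule is not repeated in the body sections.

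**Section 9.1.2** calls an event expected if it is in the Investigator's Brochure (IB), or if it is listed at the specificity or severity observed. It then names nine drug-related terms as expected, hypotension among them, and gives no severity for any. **Section 9.1.6** calls an event unexpected if it is not in the IB, or if it is not listed at the specificity or severity observed.

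**Section 9.5** makes unexpectedness one of the conditions for expedited reporting.

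**The concern.** The primary objective is safety and tolerability, and these rules are the only count-based brakes in the protocol. Two rules with matching counts and grades but different qualifying events invite different actions on the same data. A site or monitor who follows the cross-reference in Section 5.2 finds only the narrower one.

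The condition in Section 9.7.1 also works in an awkward direction. The events most plausibly caused by the drug are those already listed as expected, and these are the ones that the automatic suspension leaves out. The word *unexpected* appears to govern the Grade 4 clause as well, and Section 9.4 puts death in Grade 4.

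Finally, a trigger that rests on expectedness needs one definition of it, and the protocol has two that overlap.

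**Working it through.** The protocol states no operating characteristics for these rules, so there is no figure to reproduce. The check is a comparison of texts.

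**Step 1: the two triggers.**

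| Element | Synopsis | Section 9.7.1 |
|---|---|---|
| Grade 3 count | 2 or more patients in a dose level | 2 or more patients in a dose level |
| Grade 4 or higher count | 1 patient | 1 patient |
| Must be unexpected | No | Yes |
| Must not be due to ALF | Both grade clauses | Grade 3 clause; unclear for Grade 4 or higher |
| Action | Stops escalation (Levels 1 to 3) or drug administration (Level 4) | Suspends recruitment; MSM then SRC review |

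The counts and grades agree. The qualifying events and the actions do not.

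**Step 2: apply both to one case.** Suppose two patients in a dose level have Grade 3 hypotension SAEs that the investigator does not attribute to ALF, and the events are classed as expected.
- Synopsis: the condition is met, so escalation stops, or drug administration stops at Level 4.
- Section 9.7.1: the condition is not met, so there is no automatic suspension and no triggered review of the complete data.

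**Step 3: the two definitions.** An IB exists, so the limb for trials without one does not apply. For severity, three cases remain.

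| Event | Section 9.1.2 | Section 9.1.6 |
|---|---|---|
| Not in the IB | Not expected | Unexpected |
| In the IB, at the observed severity | Expected | Not unexpected |
| In the IB, but at a lesser severity | Expected (first limb) | Unexpected (second limb) |

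The third row is both. Each section joins its limbs with *or*. For the two to be complements, Section 9.1.2 would have to join its first two limbs with *and*.

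**Step 4: combine.** For a third-row event, Section 9.7.1 does not fire under 9.1.2 and can fire under 9.1.6. The expectedness condition for expedited reporting in Section 9.5 turns the same way. How many of the nine listed terms could fall in the third row, from 0 to 9, depends on the severities given in the IB, which is not among the documents.

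**Step 5: the ALF qualifier.** Read without it, the Grade 4 clause of Section 9.7.1 would also count unexpected Grade 4 SAEs due to ALF. That errs towards caution, but differs from the synopsis.

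**The case against.** **A deliberate two-tier design.** A stricter rule for a dose level and a narrower rule for suspending recruitment can be defended. This stands in so far as both texts can be obeyed. It does not explain the overlapping definitions, and no sentence links the tiers. The SRC charter may do so, but it is not in the documents.

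**A contradiction at Dose Level 4.** A reader might infer that the texts collide there: the synopsis stops the drug, Section 9.7.1 leaves recruitment open, and Section 6.3.2 counts a patient as enrolled only when "all eligibility criteria are met, and the study drug infusion has been initiated". The documents do not support this. Section 9.7.1 says when recruitment must be suspended, never that it must otherwise continue. If the synopsis stop covers all Level 4 dosing, Section 6.3.2 means that enrolment at that level stops with it. The synopsis could also mean only infusions already running. That is an ambiguity about new starts, not a conflict.

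**A count of patients at risk.** Section 3.3.2 says "up to 12 additional evaluable patients will be enrolled at Dose Level 4", and the synopsis says "we anticipate 25% of the enrolled population will fail to reach evaluable status", so a reader might infer 12/(1 − 0.25) = 16 treated patients exposed to the gap. That does not follow. Two must already have had the event for the Grade 3 rule (16 − 2 = 14) and one for the Grade 4 rule (16 − 1 = 15). If the stop covers all Level 4 dosing, no further patient starts at that level.

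**Evidence that the case is likely.** A reader might cite the orthostatic hypotension in the earlier dose-ranging study (Section 3.3.2). It was seen at 20 g over 4 h and above, that is 20/4 = 5 g/h or more, against 20/24 = 0.83 g/h at Level 4, a ratio of about 6. That study had no SAEs, and Section 3.3.2 says slower infusion avoids effects tied to peak concentration. Hypotension serves here only because it is on the list.

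**Existing oversight.** This stands. Sites report SAEs within 24 hours (Section 9.4), and the MSM gives an opinion on each, including expectedness, within 72 hours (Section 9.5). The MSM and the Internal Medical Monitor watch the incidence of all adverse events, and the SRC sees all safety data (Section 9.7). Section 9.7.1 also has a general net-harm criterion and keeps enrolment under ongoing review. Expected events are not hidden, but none of this settles when the automatic suspension fires.

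**Attribution.** Five of the nine terms (tachycardia, hypotension, nausea, vomiting, headache) are also on the ALF/ALI list. If the investigator attributes such an event to ALF, neither Grade 3 rule counts it. This narrows the gap but does not close it.

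**Conclusion.** The point holds as a defect of wording in a safety rule. A drug-related SAE on the expected list can stop escalation or Level 4 dosing under the synopsis without the suspension and triggered review in Section 9.7.1. For an IB-listed event of greater than listed severity, the protocol does not determine whether Section 9.7.1 fires or whether the expectedness condition for expedited reporting is met.

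The size is limited to the automatic trigger and the expectedness classification. No number of affected patients and no event probability can be derived, because the protocol gives no SAE rates and the IB severities are not available. The conclusion rests on the current text alone and assumes that the SRC charter does not already settle which rule governs. It should be fixed because the outcome now depends on the section read and the remedy is short.

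**What to change.** 1. Reword Section 9.1.2 so that an event is expected only if it is listed in the IB at the observed specificity and severity. Section 9.1.6 is then its complement.
2. In Section 9.7.1, delete *unexpected* and apply the exclusion of ALF-attributed events to both grade clauses. Make the two edits together: without the second, a Grade 4 event or death due to ALF could suspend recruitment.
3. Use this single trigger in the synopsis and Section 9.7.1. State that it stops escalation, or Level 4 dosing including new starts, and suspends recruitment pending MSM and SRC review.
4. Check the SRC charter against the new text. If dosing has already ended, report which trigger and which definition of expectedness were applied.

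The cost is one protocol amendment, with no new data or patients. The downsides are somewhat more pauses for review and possibly more events classed as unexpected, hence more expedited reports.
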